3.0 DEVICE / TECHNOLOGY DESCRIPTION

PQ Bypass designs and manufactures the PQ Bypass Guidewire Delivery System (GWDS) and the PQ Bypass Stent Graft System (SGS) and purchases the PQ Bypass Balloon Dilator (BD) from an Original Equipment Manufacturer (OEM). The GWDS is comprised of the Percutaneous Anastomotic Device (PAD) and the Venous Locator (VL) and is intended to support the delivery of guidewires in the peripheral vasculature. The SGS is comprised of a Stent Graft and a Stent Graft Delivery System and is intended to place stent grafts in the peripheral vasculature to improve blood flow. The BD is a standard percutaneous transluminal angioplasty (PTA) balloon used to dilate arterio-venous anastomoses. When used together, the GWDS, SGS and BD allow for a percutaneous bypass procedure in the peripheral vasculature.

3.1 Guidewire Delivery System (GWDS) – Percutaneous Anastomotic Device (PAD)

The PAD (**Figure 3-1**) is a spring-loaded dual guidewire delivery tool that utilizes a 0.025" Nitinol Needle with a 15 mm throw that exits approximately 45° to the PAD shaft. The PAD is an 8Fr compatible device with 135 cm working length with dual 0.014" guidewire (GW) ports; an Rx GW Port and a Needle GW Port. The Rx GW Port is a back-loaded, rapid-exchange (Rx) design used for initial device placement. The Needle GW Port is the central lumen that exits through the Needle and is used to deliver guidewires to the desired location. The PAD also incorporates an intra-luminal Stabilizer and a Platinum-Iridium Marker Band used to support and direct needle deployment, respectively. The PAD features are controlled using the Outer Handle and the Button on the PAD Handle.

[figure not shown]

Figure 3-1: Percutaneous Anastomotic Device (PAD)

The Outer Handle controls spring loading, Stabilizer deployment and Needle activation. The user rotates the Outer Handle counter-clockwise and moves it proximal to distal to load the spring, deploy the Stabilizer and activate the Needle for deployment in a single motion. The PAD Shaft is keyed to ensure that the Needle cannot be deployed without first loading the spring and deploying the Stabilizer. Subsequent depression of the Button deploys the Needle in the direction indicated by the Marker Band.

The Distal Tip of the PAD is inserted into the Distal Tip of the Venous Locator to dock the devices in the vein when creating the distal anastomosis.

Stabilizer

The Stabilizer is intended to stabilize the PAD during Needle deployment in the intra-luminal space. The Stabilizer is made of laser-cut Polyimide tubing laminated on the outer PAD Shaft. The Stabilizer is 8 mm in diameter in a deployed state (**Figure 3-2**).

[figure not shown]

Figure 3-2: Stabilizer

Needle

The Needle utilizes a lancet-point to access discrete regions of the peripheral vasculature and allow guidewire delivery. The Needle is a 0.014" guidewire compatible nickel-titanium (NiTi) tube that is heat-set with a 15 mm throw. The Needle's lancet-point design enables penetration of calcified vessels (**Figure 3-3**).

[figure not shown]

Figure 3-3: Needle Tip

Marker Band

The PAD uses a proprietary radiopaque Crown Marker Band System to orient the device prior to Needle deployment under fluoroscopy. The Crown Marker Band System (Crown System) indicates Needle direction and allows approximate adjustments in the Anterior/Posterior plane (**Figure 3-4, Figure 3-5 and Figure 3-6**).

[figure not shown]

Figure 3-4: PAD Distal Tip Assembly

[figure not shown]

Figure 3-5: Crown Marker Band System Needle Direction (directions are noted from the perspective of the device in a supine patient)

[figure not shown]

Figure 3-6: Crown Marker Band System: Direction Adjustment (Needle Direction indicated by *)

3.2 Guidewire Delivery System (GWDS) – Venous Locator (VL)

The VL (Figure 3-7) is an over-the-wire endovascular snare that utilizes dual, radiopaque NiTi cages to provide scaffold support to the femoral vein and to snare guidewires. The VL is 85 cm in length and is compatible with 7Fr sheaths and 0.014" guidewires. The dual NiTi cages deploy to a maximum of 11 mm at the apex and can be secured at a fixed diameter at any point during expansion (Figure 3-8).

Figure 3-7: Venous Locator (VL)

[figure not shown]

Figure 3-8: VL Cages Deployed

The VL is controlled using two rotating hemostasis valves (RHVs) and two handles. The Proximal Handle is connected to the Cage Hypotube which controls the retraction/deployment of the NiTi Cages. The Distal Handle allows the user to apply tension while manipulating the Proximal Handle. The Cage Hypotube runs through the Proximal RHV which is loosened to deploy/retract the NiTi Cages or tightened to lock the NiTi Cages in the desired position. The Distal RHV is connected to the Outer Shaft which slides over the retracted NiTi Cages for access, snaring and removal. The Inner Sheath defines the length of the device and provides a lumen through which the Cage Hypotube moves to allow NiTi Cage manipulation. The Inner Sheath Tip enables docking to the PAD when creating the distal anastomosis. The VL also has radiopaque markers at the proximal and distal ends of the NiTi Cages, between the NiTi Cages and at the distal tip to aide visualization during placement and deployment. The NiTi Cages are also radiopaque to enable visualization during use.

VL and PAD Docking

The Inner Sheath Tip of the VL (**Figure 3-9**) is shaped like a cone to allow docking to the PAD when creating the distal anastomosis. The user advances the PAD and VL on the same 0.014" guidewire to dock the PAD to the VL when creating a vein-to- artery anastomosis. Just as the Stabilizer is used to stabilize the PAD during Needle deployment in the intra-arterial space, docking the PAD to the VL stabilizes the PAD during Needle deployment in the intra-venous space.

[figure not shown]

Figure 3-9: Inner Sheath Tip

3.3 Stent Graft System (SGS) – Stent Graft (SG)

The PQ Bypass Stent Graft (SG) is a flexible, self-expanding composite structure made of a NiTi-wire frame encapsulated in an expanded Polytetrafluoroethylene (ePTFE) film.

The SG comes in a terminally sterile package pre-loaded on the Stent Graft Delivery System (SGDS). The SG uses a standard, crowned wire frame design that exhibits approximately twice the radial strength of commercially available stent grafts and comparable bending capability without kinking (**Figure 3-10**). The enhanced radial force helps maintain an open lumen through the proximal and distal anastomotic sites. The SG can be used either for standard intra-arterial placement or for a percutaneous bypass procedure.

Figure 3-10: PQ Bypass Stent Graft encapsulated in ePTFE

NiTi Frame:

The SG frame is a nitinol (NiTi) wire formed structure. It is made from a single 0.008" diameter NiTi wire which is shape-set and electropolished (**Figure 3-11**). The NiTi frame is a helically wrapped sinusoidal pattern with seven (7) crowns per revolution. To maintain flexibility when covered, the frame has a compression gap between adjacent helical wraps to achieve the required flexibility. Each crown has a radius with varying crown length based on the diameter of the stent graft.

Figure 3-11: NiTi Wire Frame (pictured on a process mandrel)

Stent Graft Cover:

The NiTi wire frame is completely encapsulated by the ePTFE material. The ePTFE material is made from the same base material and manufacturing processes as the ePTFE used in AAA stent grafts. It has high tensile strength and low strain and maintains excellent abrasion resistance. Due to the frame design, the cover can be applied to both the inner and outer lumen while maintaining flexibility and compressibility. The inner and outer layers of the Cover are thermally laminated together.

3.4 Stent Graft System (SGS) – Stent Graft Delivery System (SGDS)

The Stent Graft Delivery System (SGDS) is an 8Fr system. It is 0.035" guidewire compatible and has a 135 cm working length. The handle of the delivery system consists of an internal pulley mechanism activated through turning an external knob. The handle also features the fluid flush insertion point for the inner lumen. The SGDS is a familiar design which uses an outer sheath to maintain the SG in a compressed state. Once at the target site, the user can slide the outer sheath proximally by turning the knob to expose the SG which is self-expanding. The SGDS has radiopaque markers on both the proximal and distal ends of the SG landing zone (area where SG is located), as well as a marker band on the outer sheath to allow visualization of the sheath during deployment. The SGDS is shown below (**Figure 3-12**).

Figure 3-12: Stent Graft Delivery System

The outer sheath of the SGDS consists of PTFE liner, braid, and pebax layers laminated together. The proximal area of the outer sheath (area behind the SG) consists of a second layer of extrusion to reduce stretching during SG deployment.

The inner shaft of the SGDS consists of a guidewire lumen, which has a section where the SG is compressed to minimize movement during deployment. Proximal to this section, the inner shaft has a proximal stop bushing, followed by a solid wound coil, which runs the entire length of the inner shaft to the handle. The proximal stop bushing reacts to the compressive load on the inner shaft created during stent graft deployment. The coil reacts to this same load, but transfers it to the handle section, which is rigid.

The outermost sheath of the SGDS, or the tri-axial layer, isolates the outer shaft from friction induced by the valve of the introducer sheath, the vessel walls, and other sources of interference. This allows the outer shaft to be retracted with a lower deployment force, and for the SG to be deployed more accurately.

3.5 Balloon Dilator (BD)

The BD is a 4 mm by 40 mm PTA balloon used to dilate arterio-venous anastomoses during a percutaneous bypass procedure. The BD is 4Fr compatible with an OTW 0.014" guidewire port. PQ Bypass purchases the BD as a finished product from ClearStream Technologies, who designed and manufactures the BD. ClearStream Technologies commercially markets the BD as the Bantam Alpha Catheter which received its initial CE Mark in 2008 as a PTA balloon (0344). PQ bypass does not modify the device upon receipt except to label the product as the BD and provide instructions for how to utilize the product during a percutaneous bypass procedure.

4.0 PROPOSED INTENDED USE

The PQ Bypass Guidewire Delivery System is intended to support the delivery of guidewires in the peripheral vasculature.

The PQ Bypass Stent Graft System is intended to improve blood flow in patients with peripheral artery disease.

The PQ Bypass Balloon dilator is intended to dilate arterio-venous anastomoses in the peripheral vasculature.

5.0 STUDY DESIGN

5.1 Study Design

Prospective, multi-center, non-randomized study evaluating the safety and performance of the PQ Bypass Systems to access, deliver guidewires and implant stent grafts for a percutaneous femoropopliteal (fem-pop) bypass.

5.2 Study Endpoints

Primary Safety Endpoint:

Major Adverse Clinical Events (MAE) at 1 month, defined as death, target vessel revascularization (TVR), target limb amputation.

Primary Performance Endpoint:

Primary Patency at 6 month, defined as no evidence of clinically significant stenosis ($\geq 50\%$) within the stent graft or immediately above or below the treated arterial segment based on duplex ultrasound (systolic velocity ratio of >2.5), with no clinically-driven re-intervention within the stented segment.

Secondary Safety Endpoints:

- Major Adverse Events (MAE) through follow-up.
- Major adverse vascular event (MAVE) through follow-up defined as stent thrombosis, target limb amputation, clinically apparent distal embolization, defined as causing end-organ damage (e.g. lower extremity ulceration, tissue necrosis, or gangrene), procedure related arterial rupture, acute limb ischemia or bleeding event requiring transfusion.
- Major Blood Loss defined as transfusion of >2 units packed red blood cells (PRBC) through discharge.
- The combined rate of death of target vessel revascularization (TVR), index limb amputation, and an increase in Rutherford-Becker Classification by 2 classes (comparing pre- to post-procedural assessments) through follow-up.
- Deep Vein Thrombosis (DVT) on ipsilateral limb defined as a symptomatic blood clot (thrombus) in the targeted deep vein (e.g. posterior tibial) through follow-up.
- VCSS and Villalta Scale through follow-up.
- Venous Assessment (Miller Scale) through follow-up.

- Stent fracture identified via X-ray through follow-up. (Optional per standard practice. Not applicable if radiological Safety Committee approval is required e.g. BFS Germany).

Secondary Performance Endpoints:

- Technical Success defined as successful delivery of the investigational devices to the identified area and removal of delivery system.
- Procedural Success defined as successful delivery of the investigational devices to the identified area and removal of delivery system in the absence of in-hospital MAEs.
- Clinical Success defined as Limb ischemia improvement by Rutherford-Becker (improvement in scale by ≥ 1) through follow-up.
- Limb ischemia by Rutherford-Becker Classification through follow-up.
- Primary Patency through follow-up.
- Primary assisted patency defined as revascularization of non-occlusive (<99%) stenosis within the stent graft or immediately above or below the treated arterial segment with less than 50% residual stenosis through follow-up.
- Secondary patency defined as: revascularization of occlusion (100%) within the stent graft or immediately above or below the treated arterial segment with less than 50% residual stenosis through follow-up.
- Ankle-Brachial Index (ABI) through follow-up.
- Target vessel revascularization (TVR) through follow-up.
- Number of any type of index limb amputations through follow-up.
- Number of vessel run-offs through follow-up.

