11.0 ENDPOINTS AND STATISTICAL ANALYSIS PLAN

11.1 Endpoints Analyses and Reporting of Results

The study objective is to assess the safety and performance of the PQ Bypass System to access, deliver guidewires and implant stent grafts for a percutaneous fem-pop bypass.

The study is a feasibility study with no formal hypothesis testing and therefore no required sample size. Study results will be presented using descriptive statistics. Results from this study will be used to design additional clinical studies.

All subjects will be followed on an intent-to-treat basis. The device performance will be assessed based on a per-protocol analysis of the primary safety and effectiveness endpoints. An Intent-to-treat analysis, along with other secondary analyses, will also be completed and reported.

Demographic, baseline clinical and disease characteristics, procedural results and primary, secondary and all additional endpoints will be summarized using descriptive statistics.

All statistical analyses will be performed using SAS for Windows version 9.1 or higher.

Primary Safety Endpoint Reporting:

Safety assessment is achieved by recording and measuring Major Complication rates/Serious Adverse Event rates associated with the PQ Bypass procedure. The number and percentage 6-month MAE will be presented using descriptive Statistics. Using the Score approximation, the one-sided upper 95% confidence bound will be calculated and presented.

Primary Performance Endpoint Reporting:

Descriptive statistics of the primary performance endpoint which includes total number of patent PQB grafts, number and percentage of patent PQB grafts, and the one-sided 95% CI of the percentage using the Score approximation will be presented. The lower bound of the one-sided 95% CI will be compared to the performance goal of 70% (80% historical control rate – 10% Delta.)

Secondary Endpoint Analysis:

The secondary endpoint of primary assisted and secondary patency will be summarized using Kaplan-Meier survival analysis. Life tables will be created and a Kaplan-Meier survival curve will be presented.

The secondary endpoints of Procedural Success, Clinical Success and Technical

Success will be summarized by providing point estimates, number of subjects, and 95% confidence bounds calculated using the Score approximation.

Demographic, procedural and safety data:

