11.2 Sample Size Justification

The sample size chosen for this study has been updated from 60 to 100 patients. The sample size was chosen to demonstrate statistically non-inferiority of the PQ Bypass Systems performance as compared to results previously reported in similar studies:

- for intravascular stent grafts (e.g. Gore Viabahn) – n=60
- for prosthetic surgical bypass - n=100

A larger sample size is required as prosthetic surgical bypass outcomes are superior to those of intravascular stent grafts.

Stent Graft Studies

Clinical data published on existing stent graft techniques for treating femoropopliteal disease have reported 6-month primary patency rates of approximately 80%.^{37,40-42,45,60,61} This average success rate has been used as the historical control for the current study. The standard error reported in the cited studies range from 3% to 12%; the lower limit of one-sided 95% confidence intervals (CI) is approximately 68%.

In order to establish a sample size, a margin of non-inferiority, delta, was set at 10% for the current study to demonstrate non-inferiority of the PQ Bypass Systems to the historical control in terms of patency. This delta reflects the diversity of the lesions to be enrolled in this study and the range of reported performance using similar technology; 6-month primary patency in the studies cited above ranges from 27% to 92%, average lesion lengths range from 9-25cm and the percent occlusions included ranges from 50% to 100%. Due to this wide variety of lesions reported in the literature and the potential diversity of patients and lesion lengths that will be enrolled in this study, a 10% delta is adequate to accurately reflect non- inferiority. This delta sets up a comparison between the lower 95% CI of the PQ Bypass Systems performance to the lower 95% CI reported for the competitive products (~70%).

As such using as historical control rate of 80% and a non-inferiority margin of 10%,

the null and alternative hypotheses of the primary performance endpoint can be written as:

$$H_0: \pi_{PQB_performance} \leq \pi_{PG_performance}$$

$$H_A: \pi_{PQB_performance} > \pi_{PG_performance}$$

where,

$$\pi_{PG_performance} = 80\% \text{ historical control rate} - 10\% \text{ Delta}$$

$$\pi_{PQB_performance} = \text{PQB Systems success rate}$$

The hypotheses for the primary performance endpoint can be rewritten as:

$$H_0: \pi_{PQB_performance} \leq 70\%$$

$$H_A: \pi_{PQB_performance} > 70\%$$

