In order to approximate the performance rates for this study, the results from the El Camino Hospital (ECH) Study were used. The PQB procedural approach was evaluated in the ECH Study. This study used a similar technique to the interventional approach utilized in the ECH Study. This study also used a stent graft that is very similar to the stent graft used in the ECH Study, the Gore Viabahn Stent Graft. Primary patency at 6 months was approximately 90% in the ECH Study. A more conservative estimate of 85% performance for the PQ Bypass Systems was utilized along with the aforementioned performance goal for the purpose of sample size estimation. To achieve 80% power using a one-sided alpha of 0.05, the sample size is 50. To adjust for lost to follow-up and to maintain consistency with current literature on the use of stent grafts, 60 subjects will be enrolled in this study ((Table 11-1)).

Table 11-1: Non-Inferiority with PQ Bypass Performance of 85%

PG	NI Margin				
	5%	7.5%	10%	12.5%	15%
80%	103	69	50	38	30
85%	368	174	103	69	50
90%	-	1371	368	174	103
95%	-	-	-	1371	368

The sample size was also elected in order to observe the rate of major adverse events. The median number of patients enrolled in stent graft trials reported in the literature is 59 patients (range 15-144).

Surgical Bypass Studies

Clinical data published on existing surgical bypass studies for treating femoropopliteal disease is more limited quantitatively and qualitatively. Most importantly, few studies involve doppler-ultrasound assessments of arterial velocity as a basis of assessing patency (e.g. peak systolic velocity ratio). However, one particular and recent randomized prospective study of the Gore Viabahn stent graft vs. prosthetic bypass surgery provides very reliable data set on surgical outcomes as illustrated in **Table 11-2**.

The randomized prospective study was designed to compare the effectiveness of treating superficial femoral artery occlusive disease percutaneously with expanded polytetrafluoroethylene (ePTFE)/nitinol self-expanding stent grafts vs surgical femoral-to-above knee (AK) popliteal artery bypass with synthetic graft material.

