- **Q-Wave Myocardial Infarction** – Development of new, pathological Q waves in two or more contiguous leads V1-V3 or Q Wave \geq 3 ms in width in leads I, II, aVL, AVF, V4, V5 or V6 and \geq 1 mm in depth on at least two serial ECGs.
- **Non-Q-Wave Myocardial Infarction** – (1) Non-procedural (pre-procedural or $>$ 30 days post-index procedure, endovascular or surgical intervention) – CK-MB elevation \geq 2 times the upper limit of normal in the absence of new pathological Q waves, (2) post-index procedure or endovascular re-intervention (\leq 30 days) – CK-MB elevation \geq 3 times the upper limit of normal in the absence of new pathological Q waves, or (3) post-Surgical intervention ($<$ 30 days) – CK-MB elevation \geq 5 times the upper limit of normal in the absence of new pathological Q waves.

Post-Procedure ICU Time

Number of hours a patient is in an intensive care unit prior to discharge or moving to a step down or standard care unit.

Primary Assisted Patency

Revascularization of non-occlusive (<99%) stenosis within the stent graft or immediately above or below the treated arterial segment with less than 50% residual stenosis.

Primary Patency

No evidence of clinically significant stenosis (\geq 50%) within the stent graft or immediately above or below the treated arterial segment based on duplex ultrasound (systolic velocity ratio of $>$ 2.5).

Post-Procedure Length of Hospital Stay

Number of days from the end of the procedure until the patient is discharged from the hospital. This does not include time spent in a skilled care facility.

Procedural Success

Successful delivery of the investigational devices to the identified area and removal of delivery system. in the absence of in-hospital MAEs.

Procedure Time

Number of minutes needed to perform the index procedure from time of initial vessel cut down time to time of final guidewire removal. Also referred to as skin-to-skin time.

² Myocardial infarction redefined--a consensus document of The Joint European Society of Cardiology/American College of Cardiology Committee for the redefinition of myocardial infarction. Eur Heart J. 2000 Sep;21(18):1502-13. Review.

Renal Failure

Need for dialysis or a laboratory finding of serum creatinine > 3.5 mg/dL.

Respiratory Failure

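### 6-month primary patency: the re-intervention condition covers less artery than the stenosis condition and is missing from Section 19, so a bypass re-treated at its margin can count as a primary success

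*Combined protocol and SAP*

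**What the plan says.** The Protocol Summary and Section 5.2 give the same two-part definition of the primary performance endpoint. The first part requires that duplex at 6 months show no stenosis of 50% or more (velocity ratio above 2.5) in the graft or in the artery adjoining either end of the treated segment. The second part reads "with no clinically-driven re-intervention within the stented segment". The adjoining artery is in the first part and not in the second.

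The Primary Patency entry in Section 19 begins "No evidence of clinically significant stenosis", places it "within the stent graft or immediately above or below the treated arterial segment based on duplex ultrasound", and stops at the velocity ratio. It says nothing about re-intervention.

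Among the secondary endpoints, Section 5.2 lists "Primary assisted patency defined as revascularization of non-occlusive (<99%) stenosis within the stent graft or immediately above or below the treated arterial segment". Re-treatment at the margins is therefore foreseen. Secondary patency uses the same territory for occlusions.

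Section 11.1 analyses the primary endpoint as the "number and percentage of patent PQB grafts", which is a simple proportion. It then states: "The lower bound of the one-sided 95% CI will be compared to the performance goal of 70"%. It has no rule for a subject re-treated before the 6-month scan and does not say which definition governs.

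**The concern.** Consider a subject with a symptomatic stenosis just beyond one end of the graft at month 4. It is dilated, and the 6-month duplex is clean. On the 5.2 wording there is no stenosis at 6 months and there was no re-intervention inside the stented segment, so the subject can be counted as primary patent. The same subject also fits the primary assisted patency wording. Had the lesion been left alone and still been present at 6 months, the subject would have failed.

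The effect runs in one direction: margin re-treatment can add primary successes but cannot remove any. This is the only endpoint that Section 11.1 compares with a goal. The reported figure would be part primary and part assisted patency under the primary label.

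Separately, the documents hold two definitions of the primary endpoint, one with a re-intervention condition and one without.

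**Working it through.** **1. The plan's own figures.** Section 11.2 sets the margin ("a margin of non-inferiority, delta, was set at 10% for the current study") and the expected patency ("A more conservative estimate of 85% performance for the PQ Bypass Systems was utilized"), with one-sided alpha 0.05 and 80% power. The one-sample formula is n = [1.645·√(p0(1−p0)) + 0.842·√(p1(1−p1))]² / (p1−p0)².
- p0 = 0.70, p1 = 0.85: n = 49.4, rounded up to 50, as stated.
- p0 = 0.75, p1 = 0.85: n = 102.6, rounded up to 103, as stated.

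The arithmetic reproduces. The problem is in what is counted, not in the sample size.

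**2. The pass mark at n = 100.** The one-sided 95% Score lower bound is [p + z²/2n − z·√(p(1−p)/n + z²/4n²)] / (1 + z²/n), with z = 1.645 and n = 100.
- 78/100: (0.78 + 0.0135 − 0.0695)/1.0271 = 70.5%, above 70%.
- 77/100: (0.77 + 0.0135 − 0.0705)/1.0271 = 69.4%, below 70%.

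The pass mark is 78. By exact binomial tails, the chance of 78 or more is 4.8% if the true rate is 70% and 97.8% if it is 85%.

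**3. Reclassifications needed to change the result.** The count must fall to 77.
- Observed 78: 78 − 77 = 1 graft.
- Observed 85: 85 − 77 = 8 grafts.
- Observed 90: 90 − 77 = 13 grafts.

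**4. Effect on the false-pass probability.** Let q be the proportion of subjects re-treated at a margin, clean at 6 months and counted as patent. The documents give no value for q; the range below is an assumption. If strict patency (margin re-treatment counted as failure) is truly 70%, the counted rate is 70% + q.

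| q (assumed) | counted rate | chance of 78 or more of 100 |
|---|---|---|
| 0% | 70% | 4.8% |
| 1% | 71% | 7.3% |
| 2% | 72% | 10.8% |
| 3% | 73% | 15.5% |
| 5% | 75% | 28.6% |

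**The case against.** **The assisted category already takes these subjects.** A re-treated margin stenosis fits primary assisted patency, and on a hierarchical reading that is where it belongs. That is probably the intent, but nothing makes the categories exclusive, and Section 11.1 adds no such rule.

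**Absence of stenosis may be cumulative.** Arterial duplex is scheduled at discharge and at 1, 3 and 6 months, so a margin stenosis seen on an earlier scan could already be a failure. That reading would narrow the gap. The documents do not state it, and a stenosis found only on angiography would still escape a condition based on duplex.

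**The study is called descriptive.** Section 11.1 describes a feasibility study without formal testing. It also compares a confidence bound with 70%, and Section 11.2 states hypotheses. The objection lowers the severity but does not remove the point.

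**Re-treatment stays visible elsewhere.** Assisted patency, target vessel revascularization and major adverse events are reported separately. None of them feeds into primary patency.

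**The result may be far from the pass mark.** The plan assumes 85%, and Section 2.4 reports 90% at 6 months in 30 subjects. This stands: at such rates the comparison with 70% is unlikely to turn on the wording. Section 11.2 also writes the goal as 85% minus 10%, while stating 70% in the hypotheses. That is a separate inconsistency; a 75% goal would move the pass mark to 83.

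A reader might infer three stronger claims that the documents do not support:
- *Any re-opened graft counts as primary patent.* This follows only if the Section 19 entry is applied in place of Section 5.2, which excludes clinically-driven re-intervention in the stented segment. Nothing says that Section 19 overrides it.
- *The rate is biased upward against the historical control.* The table reproduced from the randomized study shows cumulative loss-of-patency events, but the documents do not say how that study treated margin re-intervention.
- *The 9 of 50 stent-graft limbs that lost patency by 6 months in that study measure the effect.* That figure counts all losses, not re-treated grafts.

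**Conclusion.** The point holds as a should-fix. The two conditions of the primary endpoint cover different territory, and Section 19 gives a conflicting definition. Under the 5.2 wording a margin lesion re-treated before a clean 6-month duplex can be counted as a primary success. This rests on reading the stenosis condition as status at 6 months, and on the undefined stented segment not including the margins; no text rules out either.

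The bias can only be upward. Its size cannot be fixed from the documents. Near the pass mark one graft decides the result; at the planned 85% it takes eight. At the null, and assuming 100 evaluable subjects and a 1% to 5% margin re-treatment rate, the false-pass probability rises from 4.8% to between 7.3% and 28.6%. Whatever the comparison shows, the label on the reported rate would not be exact.

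**What to change.** Use one definition in the Protocol Summary, Section 5.2 and Section 19. Keep the clinically-driven qualifier, but give the re-intervention condition the same territory as the stenosis condition: the graft and the artery adjoining either end of the treated segment. State that a subject with such a re-intervention before the 6-month assessment is a primary patency failure whatever the later scan shows, and is carried in assisted or secondary patency instead. Removing the clinically-driven qualifier would tighten the endpoint further; it is not needed to close this gap and is not proposed.

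Section 2.4 shows that 6-month outcomes for 30 subjects have already been seen, so also report the result under the current 5.2 wording as a sensitivity analysis.

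The cost is wording in three places, with no added subjects or visits. The procedure and follow-up lists in Section 9 name no field for where a re-intervention lay relative to the graft margins, so this must be taken from existing records. The reported rate may be slightly lower. If the rate under the current wording is truly 85%, the chance of passing falls from 97.8% to 95.7%, 87.8% or 73.9% when 1%, 3% or 5% of subjects (assumed) are reclassified.
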